5.11.3.2 Eosinophilic Disorders

Isolated cases of hypereosinophilic syndrome and drug reaction with eosinophilia and systemic symptoms have been reported. If there is clinical concern for an eosinophilic disorder, the Investigator is encouraged to contact the Medical Monitor.

Additional details regarding eosinophilia and eosinophilic disorders are provided in the bempegaldesleukin Investigator's Brochure.

5.11.4 Management Algorithms for Immune-Mediated AEs Associated with Immuno-Oncology Agents

Immuno-oncology agents are associated with AEs that can differ in severity and duration from AEs caused by other therapeutic classes. Bempegaldesleukin and nivolumab are considered immuno-oncology agents in this protocol. Early recognition and management of AEs associated with immuno-oncology agents may mitigate severe toxicity. Management Algorithms including the use of systemic corticosteroids (see the nivolumab Investigator's Brochure) have been developed to assist Investigators in assessing and managing the following groups of AEs (including, but not limited to):

- Gastrointestinal
- Renal
- Pulmonary
- Hepatic
- Endocrinopathy
- Skin
- Neurological
- Myocarditis

A management algorithm for possible signs and symptoms of CVA for patients treated with bempegaldesleukin in combination with a checkpoint inhibitor is provided in [Appendix 6](#).

5.11.5 Treatment of Bempegaldesleukin-Related or Nivolumab-Related Infusion Reactions

Infusion reactions have been reported during bempegaldesleukin and nivolumab infusions. If such a reaction were to occur with either the bempegaldesleukin or nivolumab infusion, it might manifest with fever, chills, rigors, headache, rash, pruritus, arthralgia, myalgia, hypotension, hypertension, bronchospasm, or other hypersensitivity/allergic-like reactions. Infusion reactions should be graded as outlined below (consistent with Common Terminology Criteria for Adverse Events [CTCAE] version 5.0 grading of infusion-related reaction); please also refer to Section [8.3](#).

Treatment recommendations are provided below and may be modified based on local treatment standards and guidelines, as appropriate:

For **Grade 1** symptoms (mild reaction; infusion interruption not indicated; intervention not indicated):

- Remain at the bedside and monitor the patient until recovery from symptoms. The following prophylactic premedications are recommended for future infusions: diphenhydramine 50 mg (or equivalent) and/or acetaminophen/paracetamol 325 to 1000 mg at least 30 minutes before subsequent infusions.

For **Grade 2** symptoms (moderate reaction requires therapy or infusion interruption but responds promptly to symptomatic treatment [e.g., antihistamines, nonsteroidal anti-inflammatory drugs, narcotics, corticosteroids, bronchodilators, IV fluids]; supportive medications indicated for ≤ 24 hours):

- Stop the bempegaldesleukin or nivolumab infusion, begin an IV infusion of normal saline, and treat the patient with diphenhydramine 50 mg IV (or equivalent) and/or acetaminophen/paracetamol 325 to 1000 mg; remain at the bedside and monitor the patient until resolution of symptoms. Corticosteroid and/or bronchodilator therapy may also be administered as appropriate. If the infusion is interrupted, then restart the infusion at 50% of the original infusion rate when symptoms resolve. If symptoms recur after restarting the bempegaldesleukin or nivolumab infusion, then no further bempegaldesleukin or nivolumab will be administered at that visit. Administer diphenhydramine 50 mg IV, remain at the bedside, and monitor the patient until resolution of symptoms.
- For future infusions, the following prophylactic premedications are recommended: diphenhydramine 50 mg (or equivalent) and/or acetaminophen/paracetamol 325 to 1000 mg should be administered at least 30 minutes before the infusion. If necessary, corticosteroids (up to 25 mg of methylprednisolone or equivalent) may be used (see [Appendix 5](#) for corticosteroid dose equivalents).

For **Grade 3 or Grade 4** symptoms (severe reaction, Grade 3: prolonged [i.e., not rapidly responsive to symptomatic medication and/or brief interruption of infusion], recurrence of symptoms following initial improvement, hospitalization indicated for other clinical sequelae [e.g., renal impairment, pulmonary infiltrates]; Grade 4: life-threatening [pressor or ventilatory support indicated]):

- Immediately discontinue infusion of bempegaldesleukin or nivolumab. Begin an IV infusion of normal saline and treat the patient as follows: recommend bronchodilators, epinephrine 0.2 to 1 mg of a 1:1000 solution for subcutaneous administration or 0.1 to 0.25 mg of a 1:10,000 solution injected slowly for IV administration, and/or diphenhydramine 50 mg IV with methylprednisolone 100 mg IV (or equivalent), as needed.
- The patient should be monitored until the Investigator is comfortable that the symptoms will not recur. Investigators should follow their institutional guidelines for the treatment of anaphylaxis. Remain at the bedside and monitor the patient until recovery of the symptoms.

In case of late-occurring hypersensitivity symptoms (e.g., appearance of a localized or generalized pruritus within 1 week after treatment), symptomatic treatment may be given (e.g., oral antihistamine or corticosteroids).

5.11.6 Management Algorithm for Cytokine Release Syndrome

Cytokine-release syndrome (CRS) is a clinical diagnosis with a constellation of symptoms often characterized by fever, tachypnea, headache, tachycardia, hypotension, rash, and/or hypoxia caused by the release of cytokines. In addition, diarrhea and end organ dysfunction can be seen in CRS. Many of these symptoms overlap with known AEs seen in bempegaldesleukin and nivolumab combination therapy (i.e., pyrexia and hypotension). These symptoms may be seen in infusion reactions as well as other known syndromes, such as tumor lysis syndrome and macrophage activation syndrome. For suspected CRS of Grade 3 or above, the Investigator is encouraged to contact the Sponsor. An algorithm for the management of CRS is provided in [Appendix 7](#).

5.12 Discontinuation Criteria

Bempegaldesleukin combined with nivolumab treatment or nivolumab monotherapy must be permanently discontinued for the following:

- Patient's request to stop study treatment. Patients who request to discontinue study treatment will remain in the study and must continue to be followed for protocol-specified follow-up procedures. The only exception to this is when a patient specifically withdraws consent for further assessments or contact with him/her or persons previously authorized by patient to provide this information.
- Loss of ability to freely provide consent through imprisonment or involuntarily incarceration for treatment of either a psychiatric or physical (e.g., infectious disease) illness. (Note: Under specific circumstances, a patient who has been imprisoned may be permitted to continue as a patient. Strict conditions apply and Sponsor approval is required.)

- Any clinical AE, laboratory abnormality or intercurrent illness which, in the opinion of the Investigator, indicates that continued participation in the study is not in the best interest of the patient.
- Noncompliance of the patient with protocol-mandated procedures based on the judgment and agreement of both the Investigator and Sponsor.
- See additional study treatment discontinuation criteria specific to bempegaldesleukin- or nivolumab-related AEs (Section 5.12.1).
- Termination of the study by the Sponsor.
- Disease recurrence (local, regional, or distant), including new primary melanoma (except MMIS Stage 0)

Note: Non-melanoma skin cancer does not require treatment discontinuation. In the absence of intolerable toxicity, patients with diagnosed MMIS Stage 0 melanoma will be eligible to continue study treatment using the same dose and schedule for their original melanoma of up to approximately 1 year of study treatment starting from first dose, at the discretion of the Investigator.

- Lost to follow-up (defined as after three attempts at contact by phone followed by one attempt by sending a certified letter).

If a patient has not experienced disease recurrence following discontinuation of study drug(s), every effort should be made to continue to obtain radiographic tumor assessments as outlined in Section 7.1.

A patient may also be withdrawn from investigational product/study by the Sponsor, Regulatory Authorities, or IRBs/ IECs.

Patients may choose to discontinue the study at any time, for any reason, and without prejudice to further treatment.

Refer to the Schedule of Events (Section 1.2) for data to be collected at the time of treatment discontinuation and follow-up and for any further evaluations that can be completed.

In the case of pregnancy, the Investigator must immediately, within 24 hours of awareness of the pregnancy, notify the Sponsor of this event. If a female patient becomes pregnant, administration of the study drug(s) must be discontinued immediately. Refer to Section 8.13.2 (Pregnancy).

All patients who discontinue study treatment should comply with protocol-specified follow-up procedures as outlined in Section 1.2. The only exception to this requirement is when a patient withdraws consent for all study procedures including post-treatment study follow-up or loses the ability to consent freely (i.e., is imprisoned or involuntarily incarcerated for the treatment of either a psychiatric or physical illness).

If study treatment is discontinued prior to the patient's completion of the study, the reason for the discontinuation must be documented in the patient's medical records and entered on the CRF page.

5.12.1 Discontinuation Criteria for Treatment-Related Toxicities

Patients meeting any of the following criteria will be required to permanently discontinue all assigned study drug(s). In Arm A, per Investigator assessment, treatment with bempegaldesleukin or nivolumab alone may continue if a toxicity meeting discontinuation criteria below is considered related to one and not the other study drug and once the criteria to resume treatment are met (Section 5.10.3).

Study treatment should be permanently discontinued for the following:

- Any Grade ≥ 2 treatment-related uveitis, eye pain, or blurred vision that does not respond to topical therapy and does not improve to Grade 1 severity within 8 weeks or requires systemic treatment.
- Any Grade ≥ 2 treatment-related pneumonitis or interstitial lung disease that does not resolve following dose delay and systemic steroids (also see Pulmonary Adverse Event Management Algorithm in the nivolumab Investigator's Brochure).
- For Grade ≥ 3 adrenal insufficiency or Grade ≥ 4 hypophysitis, treatment needs to be discontinued regardless of control with hormone replacement (Note: Hospitalization for diagnostic workup of adrenal insufficiency without severe symptoms should not require discontinuation).
- Any Grade ≥ 3 non-skin, treatment-related AE lasting > 7 days or recurs, with the following exceptions for uveitis, pneumonitis, bronchospasm, diarrhea, colitis, neurologic toxicity, hypersensitivity reactions, infusion reactions, endocrinopathies, and laboratory abnormalities:
 - Grade 3 treatment-related uveitis, pneumonitis, bronchospasm, diarrhea, colitis, neurologic toxicity, hypersensitivity reaction, or infusion reaction of any duration requires discontinuation.
 - Grade 3 treatment-related endocrinopathies (excluding adrenal insufficiency and hypophysitis) adequately controlled with only physiologic hormone replacement do not require discontinuation.
 - Grade 3 treatment-related laboratory abnormalities do not require treatment discontinuation except:
 - Grade 3 treatment-related thrombocytopenia > 7 days or associated with clinically significant bleeding requires discontinuation.
- In most cases of Grade 3 AST or ALT elevation, study treatment will be permanently discontinued. If the Investigator determines a possible favorable benefit/risk ratio that warrants continuation of study treatment, a discussion between the Investigator and the Medical Monitor/designee must occur. For IL-2 mediated ALT/AST elevations $< 8.0 \times \text{ULN}$ in Cycle 1 only, study treatment does not need to be discontinued (see Section 5.10.2).

- Any treatment -related liver function test abnormality that meets the following criteria require discontinuation (also see Hepatic Adverse Event Management Algorithm in the nivolumab Investigator's Brochure):
 - AST or ALT $> 5 \times$ ULN to $8 \times$ ULN for > 2 weeks
 - AST or ALT $> 8 \times$ ULN
 - Total bilirubin $> 5 \times$ ULN
 - Concurrent AST or ALT $> 3 \times$ ULN and total bilirubin $> 2 \times$ ULN
- Grade 3 or 4 infusion reaction of any duration:
 - For Arm A: If infusion reaction occurs during the bempegaldesleukin infusion or prior to the nivolumab infusion, discontinuation of bempegaldesleukin is required.
 - For Arm A: If infusion reaction occurs during the nivolumab infusion or later, discontinuation of both bempegaldesleukin and nivolumab is required.
- Any Grade 4 treatment -related AE or laboratory abnormality, except for the following events, which do not require discontinuation:
 - Grade 4 neutropenia ≤ 7 days.
 - Grade 4 lymphopenia or leukopenia ≤ 14 days in duration.
 - Isolated Grade 4 amylase or lipase abnormalities that are not associated with symptoms or clinical manifestations of pancreatitis and decrease to Grade < 4 or return to baseline within 7 days.
 - Isolated Grade 4 electrolyte imbalances/abnormalities that are not associated with clinical sequelae and are corrected with supplementation/appropriate management within 72 hours of their onset.
 - Grade 4 treatment -related endocrinopathy AEs (except adrenal insufficiency or hypophysitis), such as hyper- or hypothyroidism, or glucose intolerance, which resolve or are adequately controlled with physiologic hormone replacement (corticosteroids at ≤ 10 mg of prednisone or equivalent per day, thyroid hormones) or glucose-controlling agents, respectively, may not require discontinuation after discussion with and approval from the Medical Monitor.
- Any AE, laboratory abnormality, or intercurrent illness that, in the judgment of the Investigator, presents a substantial clinical risk to the patient with continued treatment.
- Arm A only: Any new CVA event confirmed by diffusion-weighted imaging MRI, regardless of neurological symptoms (e.g., cryptogenic CVA) and for suspected TIA without clear alternative etiology (see [Appendix 6](#))

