5.10.1.2 Arm A or Arm B: Nivolumab Dose Delay Criteria

If nivolumab meets the criteria for dose delay, then administration of both drugs (for patients on Arm A) must be delayed until the criteria to resume are met.

Nivolumab administration should be delayed for the following:

- Grade 2 non-skin, treatment-related AE, with the exception of fatigue
- Grade 2 treatment-related creatinine, AST, ALT, and/or total bilirubin abnormalities

- Grade 3 skin, treatment-related AE
- Grade 3 treatment-related laboratory abnormality, with the following exceptions:
 - Grade 3 lymphopenia or asymptomatic amylase and/or lipase abnormalities do not require dose delay
 - Grade ≥ 3 AST, ALT, total bilirubin will require dose discontinuation (unless satisfying the Cycle 1 AST/ALT elevation criteria outlined in Section 5.10.2)
- Any AE, laboratory abnormality, or intercurrent illness which, in the judgment of the Investigator, warrants delaying the dose of study medication.

Patients who require delay of nivolumab should be re-evaluated weekly or more frequently if clinically indicated and resume nivolumab dosing when retreatment criteria are met. Dose reductions for nivolumab are not permitted in this study.

5.10.2 Dose Modification Criteria for Bempegaldesleukin and Nivolumab for Cycle 1 ALT/AST Elevations

The following recommendations are for Cycle 1 only and are not intended to serve as rigid guidelines or to replace clinical judgment. Subsequent cycles should follow standard Hepatic Adverse Event Management Algorithm in the nivolumab Investigator's Brochure.

Rule out alternative etiologies. Consider imaging if obstruction is suspected. If there is a non-inflammatory etiology, treat accordingly and continue bempegaldesleukin and nivolumab.

If ALT/AST increases during monitoring, follow the guidance for the highest levels.

AST or ALT > 3.0 to $\leq 5 \times$ ULN (within first cycle of bempegaldesleukin plus nivolumab)

Increase frequency of liver function test monitoring to approximately every 3 days and delay treatment until lab abnormalities resolve to Grade 0 to 1.

If no improvement within 7 days, treat with 0.5 to 1 mg/kg/day prednisone equivalents, and taper steroids over at least 1 month before resuming treatment.

ALT or AST > 5.0 to $\leq 8.0 \times$ ULN (within first cycle of bempegaldesleukin plus nivolumab)

Increase frequency of monitoring to approximately every 3 days until lab abnormalities resolve to Grade 0 to 1.

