Treatment must be delayed until lab abnormalities resolve to Grade 0 to 1.

If no improvement within 7 days (follow the Hepatic Adverse Event Management Algorithm in the nivolumab Investigator's Brochure):

- Discontinue bempegaldesleukin plus nivolumab

- 1 to 2 mg/kg/day prednisone equivalents followed by corticosteroid taper over at least one month
- Consult gastroenterologist
- Consider adding non-corticosteroid immunosuppressive medication if no improvement in > 3 to 5 days, worsens or rebounds while on steroids

ALT or AST > 8.0 × ULN (follow Hepatic Adverse Event Management Algorithm in the nivolumab Investigator’s Brochure)

- Discontinue bempegaldesleukin plus nivolumab
- Increase frequency of monitoring to approximately 1 to 2 days
- 1 to 2 mg/kg/day prednisone equivalents followed by corticosteroid taper over at least one month
- Consult gastroenterologist
- If no improvement in > 3 to 5 days, worsens or rebounds, add non-corticosteroid immunosuppressive medication

Please refer to Section 5.12.1 for discontinuation criteria.

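### After Cycle 1, Grade 3 AST/ALT is a mandatory stop in Protocol Section 5.10.1.2 but a discretionary one in Section 5.12.1; the Cycle 1 exemption also has two loose ends

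*Protocol*

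**What the plan says.** Three parts of the protocol deal with stopping for AST/ALT.

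- **Section 5.10.1.2** (nivolumab dose delay, both arms). Grade 3 or higher "AST, ALT, total bilirubin will require dose discontinuation", "unless satisfying the Cycle 1 AST/ALT elevation criteria outlined in Section 5.10.2". No other exception is given.
- **Section 5.10.2** (Cycle 1 elevations). Its recommendations "are for Cycle 1 only and are not intended to serve as rigid guidelines or to replace clinical judgment". Above 5.0 and up to and including 8.0 x ULN, the first step is "Treatment must be delayed until lab abnormalities resolve to Grade 0 to 1". The next step begins "If no improvement within 7 days (follow the Hepatic Adverse Event Management Algorithm" and its action is "Discontinue bempegaldesleukin plus nivolumab". Above 8.0 x ULN, both drugs are stopped.
- **Section 5.12.1** (discontinuation for toxicity). Meeting any listed criterion obliges the patient to stop. Among the items:
  - Grade 3 AST/ALT usually leads to permanent discontinuation. An investigator who sees a favourable benefit/risk balance may continue after discussion with the Medical Monitor.
  - For IL-2 mediated elevations below 8.0 x ULN, "in Cycle 1 only, study treatment does not need to be discontinued", with a pointer to 5.10.2.
  - The next bullet requires a stop for AST or ALT above 5 and up to 8 x "ULN for > 2 weeks", for any value above 8 x ULN, and for a value above 3 x ULN together with total bilirubin above 2 x ULN.

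**The concern.** A site with a Grade 3 transaminase result in Cycle 2 or later can find a compulsory stop in one section and a route to continue in another. Neither section refers to the other on this point.

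The situation is foreseeable. Section 5.11.1 describes transaminase elevation as a toxicity shared by both drugs. It says that the bempegaldesleukin-associated elevations arise mainly in Cycles 1 and 2, and Cycle 2 is outside the carve-out. The 5.10.2 bands up to 8 x ULN are also worded for the combination, so on their face they do not give Arm B the exception, although 5.10.1.2 applies to both arms.

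At stake are patient safety, avoidable loss of treatment, and comparability between sites. If stopping depends on which section a site reads, the SAP summaries of events leading to discontinuation (Section 7.1), disposition by reason (Section 6.8) and exposure (Section 6.10.2) partly reflect that reading.

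**Working it through.** There is no design figure to reproduce. The check is to take the same laboratory result through each rule as written.

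**Inputs.** The rules are those set out above. One assumption is needed for the examples in rows 1 to 3 and 7: Grade 3 AST/ALT starts above 5 x ULN. The protocol names CTCAE version 5.0 but does not print the cut-off. Results are taken as treatment-related, without improvement, and without a raised bilirubin. Cycle 1 results are taken as IL-2 mediated in Arm A.

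| | Result | 5.10.1.2 | 5.10.2 | 5.12.1, Grade 3 text and exemption | 5.12.1, next bullet |
|---|---|---|---|---|---|
| 1 | Cycle 3, 6 x ULN, 10 days | Stop required | Not applicable | Usually stop; may continue after discussion | Not met |
| 2 | Cycle 3, 6 x ULN, 16 days | Stop required | Not applicable | As row 1 | Stop required |
| 3 | Cycle 3, 9 x ULN, 3 days | Stop required | Not applicable | As row 1 | Stop required |
| 4 | Cycle 1, 6 x ULN, 5 days | Defers to 5.10.2 | Delay | Stop not needed; see 5.10.2 | Not met |
| 5 | Cycle 1, 6 x ULN, 10 days | Defers to 5.10.2 | Stop both drugs | Stop not needed; see 5.10.2 | Not met |
| 6 | Cycle 1, 6 x ULN, 16 days | Defers to 5.10.2 | Stop both drugs | Stop not needed; see 5.10.2 | Stop required |
| 7 | Cycle 1, exactly 8.0 x ULN, 5 days | Defers to 5.10.2 | Delay | Exemption does not apply; usually stop | Not met |

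**After Cycle 1 (rows 1 to 3).** Row 1 is the conflict. Rows 2 and 3 show its limits: beyond 2 weeks in the band, or above 8 x ULN, the next bullet of 5.12.1 also requires a stop and the outcome agrees. The disagreement therefore covers Grade 3 results outside the carve-out, up to 8 x ULN, lasting no more than 2 weeks, without the bilirubin criterion. A different Grade 3 cut-off would move the example value but not the clash, which is between two statements about Grade 3 as such.

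**Cycle 1 (rows 4 to 7).** Row 4 is consistent. In row 5 the exemption sentence and the 7-day step differ unless the pointer to 5.10.2 is read as making the exemption subject to that step; the text does not say so. In row 6 the exemption and the bullet that follows it, both in 5.12.1, differ, because the bullet states no Cycle 1 exception. Rows 5 and 6 use thresholds given directly in multiples of ULN and need no grade cut-off. Row 7 is a boundary mismatch: 5.10.2 includes 8.0, and the exemption stops short of it.

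**The case against.** The strongest reply is that the protocol says where its stopping criteria are. Sections 5.4 and 5.10 both send the reader to 5.12, and 5.10.2 closes by pointing to 5.12.1. On that view, the clause in 5.10.1.2 is a loose summary inside a dose-delay section, and 5.10.2 is advisory by its own description. This has weight, but the pointers locate the criteria without cancelling the mandatory sentence in 5.10.1.2. That sentence sets its own single exception and leaves no room for the discussion that 5.12.1 allows.

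For Cycle 1 the reply is largely right. A reader might infer a three-way contradiction: stop after 7 days, never stop below 8 x ULN, or stop only after 2 weeks. The documents do not support that.

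- The exemption is limited to IL-2 mediated elevations and refers to 5.10.2, which contains the 7-day step.
- The 2-week bullet does not say that stopping is confined to that case. The 5.12.1 criteria are cumulative, so one that is not met does not permit continuation.
- The two time limits measure different things, failure to improve and persistence in the band, and can operate in sequence.

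Sections 5.10.1.2 and 5.10.2 also do not conflict with each other in Cycle 1, because the first defers to the second.

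Finally, several passages rely on the hepatic algorithm in the nivolumab Investigator's Brochure, which is not among the documents. It may have given sites clearer instructions, but it would not remove the inconsistency within the protocol.

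**Conclusion.** The inconsistency is real and narrow. For Grade 3 AST/ALT outside the Cycle 1 carve-out, stopping is compulsory in 5.10.1.2 and discretionary in 5.12.1. Because 5.10.1.2 is a nivolumab section, the direct clash concerns nivolumab, in both arms. The Cycle 1 points are secondary: an exemption that does not state its relation to the 7-day and 2-week stops, and a mismatch at exactly 8.0 x ULN.

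The size cannot be given, since the documents do not report how often such elevations occur. The 950 patients, 400 events and 94% power are untouched. SAP Sections 2.0 and 6.11 record that the programme was ended in April 2022 and that no comparative analyses will be done, so the practical consequence now is for reading the descriptive summaries by arm and for any reuse of this text. The main conflict rests on wording alone; the Grade 3 cut-off is assumed for the worked examples only. No view is taken on which rule is clinically right.

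**What to change.** Reconcile Sections 5.10.1.2, 5.10.2 and 5.12.1 so that each combination of AST/ALT band, cycle and duration leads to one instruction, and state which section governs where they differ. In doing so:

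- settle whether Grade 3 outside the Cycle 1 carve-out is a mandatory or a discretionary stop, and use the same wording in both places;
- say whether the IL-2 mediated Cycle 1 exemption is subject to the 7-day step and to the 2-week criterion;
- use the same boundary at 8.0 x ULN throughout;
- say whether the Cycle 1 carve-out applies to Arm B.

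The clinical team must choose the rules. The cost is protocol wording and a clarification to sites. For a report on the data already collected, a sentence noting the inconsistency beside the discontinuation, disposition and exposure tables would be enough. No analysis has to be redesigned.
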